3.9.2 Definition of MOH during the trial

Panel 4 IHS ICHD-3 Guidelines for MOH

- A. Headache occurring on ≥ 15 days/month in a patient with a pre-existing headache disorder
- B. Regular overuse for >3 months of one or more drugs that can be taken for acute and/or symptomatic treatment of headache
- C. Not better accounted for by another ICHD-3 diagnosis

Regular overuse is defined either on:

- 10 days of use/month or more for >3 months of ergotamine, triptan, opioid (butorbital in US), or combination of analgesics
- 15 days of use/month or more for >3 months of non-opioid analgesics (paracetamol [acetaminophen], acetylsalicylic acid, NSAIDs)

In [Panel 4](#) above, the IHS ICHD-3 Guidelines for MOH are stated and used to confirm the MOH diagnosis at the screening visit.

During the trial, to evaluate whether a participant continues to overuse acute migraine medication, the eDiary data will be used for a specific post-baseline 4-week period (28-day period) only and the steps below will be followed:

Check acute migraine medication overuse in the reported month.

Count the number of days on which a medication was taken to treat a headache for each pre-defined acute migraine medication in the reported month (28-days period).

If the participant meets any of the following criteria in the reported month, the participant is considered as overusing acute migraine medication, used as “MOH” in the endpoint definitions. N is the number of monthly days.

- $N \geq 10$ days with either ergotamine, or $N \geq 10$ days with triptan
- $N \geq 10$ days with combination of two or more drug classes among ergotamine, triptan, opioid analgesic and non-opioid analgesics
- $N \geq 10$ days on which combination analgesics are taken.
- $N \geq 15$ days on which a non-opioid analgesic (paracetamol, acetylsalicylic acid, NSAIDs, analginum, antipyrine, tolfenamic acid) is taken. The overuse could be with a single non-opioid analgesic or with several of them.

4 Analysis Sets

The following analysis sets will be used to analyse and present the data:

- *all-participants-screened set (APSS)*
- *all-participants-randomized set (APRS)* – all randomized participants
- *all-participants-treated set (APTS)* – all participants in the APRS who received an infusion of the IMP in the Placebo-controlled Period
- *full-analysis set (FAS)* – all participants in the APTS who had a valid baseline assessment and at least one valid post-baseline 4-week assessment of MMDs in Weeks 1-12

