- *all-participants-treated-open-label set (APTS-OL)* – all participants in the APRS who received an infusion of the IMP in the Open-label Period
- *all-participants-treated-follow-up set (APTS-FU)* - All participants in the APTS who are not in the APTS-OL, and who have data collected from the Safety Follow-up visit.

All data from the Placebo-controlled Period will be cleaned and the trial database for the Placebo-controlled Period will be locked when all participants have either completed or been withdrawn from the Placebo-controlled period. The participants and data will be classified into the analysis sets (APRS, APTS, and FAS) at a *Classification Meeting* held after the trial database for the Placebo-controlled Period has been released.

Data will be unblinded after the *Classification Meeting* for the sponsor and CRO functions involved in performing the analysis. All analyses specified in the SAP for data collected in the

Placebo-controlled Period will be performed. Sponsor and CRO functions that are in contact with the trial site staff, as well as clinical site staff and participants will remain blinded to individual participant treatment assignment through the end of the trial.

After all participants have completed the Open-label Period, the trial database for the full trial will be cleaned and locked. The participants and data will be classified into the analysis sets (APTS-OL and APTS-FU) according to these definitions. The defined population sets will be reviewed at a second *Classification Meeting* held after the full trial database has been released. The CTR will be issued after the end of the full trial completion.

Unless otherwise specified, the FAS will be used for all efficacy analyses in the Placebo-controlled Period, and the APTS will be used for all safety analyses in the Placebo-controlled Period, while the APTS-OL will be used for the safety and efficacy analysis of the Open-label Period. Relevant safety outputs for data collected at the Safety Follow-up visit for the APTS-FU will be listed.

5 Descriptive Statistics

In general, summary statistics (n, arithmetic mean, standard deviation [SD], median, lower and upper quartiles, minimum and maximum values) will be presented for continuous variables and counts and, if relevant, percentages will be presented for categorial variables.

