11.1 General Efficacy Analysis Methodology

All the tables and graphs will be presented by treatment group for the Placebo-controlled Period and by treatment sequence for the Open-label Period. Unless otherwise specified, all the efficacy

analyses for the Placebo-controlled Period will be based on the FAS and all the efficacy analyses for the Open-label Period will be based on the APTS-OL.

All the statistical tests of the efficacy endpoints will be two-sided tests performed at the 5% significance level and all CIs will be 95% CIs, unless otherwise specified. Details of the imputations used for the eDiary data can be seen in the rules for handling missing data described in Section 15.14.1. Only descriptive summaries will be presented for the efficacy analyses for the Open-label Period.

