11.3.4 Sensitivity Analyses of the Primary Endpoint

11.3.4.1 Assessing the impact of missing data using a pattern-mixture model

A sensitivity analysis using the placebo-based multiple imputation (pMI) method to assess the robustness of the conclusions for this endpoint with respect to the missing data will be conducted. Specifically, an analysis will be performed using a pattern-mixture model (PMM), in which the remaining missing data after application of the prorating rule, see Section 15.1.1, will be imputed using a sequential regression-based multiple imputation method, based on the imputation models established from the PBO group.² As the missing not at random (MNAR) strategy chosen will impute all missing data for participants treated with eptinezumab, as if they were treated with placebo, this is considered to be a conservative approach.

200 simulations will be performed to generate the datasets that will be analysed using the model described in Section 11.3.2. These analyses will be combined using Rubin's rule to form a unique point estimate and standard error, taking into account the uncertainty of the imputation.

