11.3.4.2 Assessing the impact of missing data using a tipping point analysis

To further evaluate the potential impact of missing data, a multiple imputations (MI) approach will be used to impute the missing data for all three 4-week post-baseline periods in the Placebo-controlled Period using a tipping point analysis, where the robustness of the results under

increasing deviations from missing at random (MAR) for the missing observations will be assessed.

After the use of prorating, the remaining missing data for each month will firstly be imputed through standard MI under MAR assumption. In addition, the imputed data for MMDs on eptinezumab for each 4-week post-baseline period will be adjusted by applying a range of deviations based on delta (δ) and the estimated effects for EPTI and PBO for each 4-week post-baseline period from primary analysis as follows:

$$\text{EPTI} + \delta \cdot (\text{PBO} - \text{EPTI}),$$

where δ will take values 0%, 10%, 20%, 30%, ...

Thus, the estimated effect will start from an assumption of the effect being similar to the effect in other participants treated with EPTI, and then stepwise worsen, with $\delta = 100\%$ being an assumption of participants with missing data having a similar effect as placebo. The value of δ will be increased until the p-value > 0.05 , or until the limit for the worst score possible for the missing data has been reached. In case of monthly migraine days, the score cannot be worse than 28 days with migraine out of 28 days observed. The method used for imputation, analysis of data and combination of results from analyses will match the pMI method described above (same seed numbers will also be used), except for the assumed effect for the EPTI group which will be as described in this section.

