15.1.1 Monthly Migraine Days /Monthly Headache Days

The following describes the derivation of MMDs. The derivation of MHDs follows the same principles. Definitions of a migraine day and a headache day are described in Section 3.6.

Pooling of symptoms

To assess whether a headache is a migraine headache, daily reported symptoms will be pooled to assess the migraine criteria described in Section 3.6. The worst reported symptom will be used, for example, if different levels of worst pain have been reported on different days of the same headache, the worst of these levels will be used to assess the migraine criteria.

Regarding successful medication use for the criterion “a headache that is successfully treated with a triptan, ergotamine, or other migraine-specific acute medication”: a medication can only be considered successful if the question *“Did at least one of the medications you took today successfully treat your headache?”* is answered positively on the same day as the medication intake date.

4-Week Intervals

For Baseline and each 4-week period post-baseline in the trial, the number of MMDs will be derived as the number of migraine days within each 28-day interval using the imputation rules described below. The 4-week periods post-baseline that are considered are the following: Weeks 1-4, Weeks 5-8, Weeks 9-12, Weeks 13-16, Weeks 17-20 and Weeks 21-24.

In general, for 4-week periods where the number of reported eDiary days are at least 14 days out of the 28 days, prorating will be used to calculate the MMDs, and for 4-week periods where the number of reported eDiary days are less than 14 days out of the 28 days, the MMDs will be set to missing. Once prorating has been applied, a non-missing 4-week MMD value is considered a valid assessment.

Prorating

Intended to be used for 4-week periods where the eDiary is completed on at least 14 out of the 28 days, the prorating procedure consists of imputing days with missing information with the observed mean number of migraine days in the period as follows:

$$28^*(\text{Reported Migraine Days}/\text{Reported eDiary Days})$$

This imputation rule will also be used for the Baseline value regardless of the number of reported eDiary days in the screening period.

When the number of MMDs have been calculated for a given 4-week period, the result will be rounded to two decimals.

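### The missing-data sensitivity analyses for Weeks 1-4 run on the FAS by default and so omit treated participants with no valid post-baseline month

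*SAP*

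**What the plan says.** SAP 11.3.4 plans two missing-data sensitivity analyses for the primary endpoint.

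- **Placebo-based multiple imputation (pMI), 11.3.4.1.** "the remaining missing data after application of the prorating rule, see Section 15.1.1, will be imputed using a sequential regression-based multiple imputation method". The models used for this come from the placebo arm alone; values are drawn "based on the imputation models established from the PBO group".
- **Tipping point, 11.3.4.2.** "After the use of prorating, the remaining missing data for each month will firstly be imputed through standard MI under MAR assumption". The imputed eptinezumab values are then worsened step by step.

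Neither subsection names an analysis set. The default is stated in SAP section 4, "the FAS will be used for all efficacy analyses in the Placebo-controlled Period", and again in SAP 11.1, "analyses for the Placebo-controlled Period will be based on the FAS". Protocol 16.2 and 16.8.1 agree.

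SAP section 4 defines the FAS as "all participants in the APTS who had a valid baseline assessment and at least one valid post-baseline 4-week assessment of MMDs in Weeks 1-12". SAP 15.1.1 decides what is valid: where the number of reported diary days is "less than 14 days out of the 28 days, the MMDs will be set to missing". Baseline is treated differently: "This imputation rule will also be used for the Baseline value regardless of the number of reported eDiary days in the screening period". A missing baseline will therefore rarely exclude anyone; the post-baseline condition does.

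**The concern.** A treated participant who stops the diary before 14 reported days and then withdraws has no valid Month 1, 2 or 3. That person is outside the FAS and is removed before any imputation. Within the FAS, a Weeks 1-4 value can be missing only for someone who missed Month 1 and then supplied a valid Month 2 or 3. For the primary contrast, both analyses thus examine intermittent gaps and leave out early permanent loss, where departures from missing at random are most plausible.

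This fits poorly with the plan's own aims. SAP 11.3.4.1 describes the strategy as imputing every missing value in the eptinezumab arm and calls it conservative. Protocol chapter 2 defines the estimand population as the whole study population, not those with a valid month.

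Early loss could also be related to outcome or arm. Protocol 1.1.1 describes rebound headache and withdrawal symptoms lasting about 2 to 3 weeks. Protocol 1.1.3 reports hypersensitivity reactions in about 3% on 100 mg and 1% on placebo. Such patients are encouraged to stay, so how many leave is unknown.

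At stake is the scope of the claim: a statement that the Weeks 1-4 result is robust to missing data would not extend to these participants.

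**Working it through.** **The plan's own figure.** SAP section 14 assumes an effect of -1.5, SD 6.2, two-sided 5% and 80% power. The normal formula 2 × 6.2² × (1.96 + 0.8416)² / 1.5² gives 268.2, so 269 per group. With the t distribution, power is 79.98% at 269 and 80.1% at 270, so the stated 270 reproduces. 270/0.95 = 284.2, rounded up to 285, also reproduces.

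**Assumptions.** The documents do not say how many treated participants lack a valid month. I take N = 285 treated per arm and m = 3, 9 or 14 per arm with no valid month (about 1%, 3% and 5%), equal in both arms. The 5% in SAP section 14 is a general allowance for not contributing data, so 14 is an upper assumption. The calculation treats Month 1 alone, without covariates.

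**Formulas** (effects as absolute values)

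- FAS standard error: 6.2 × √(2/(285 − m)). The significance threshold is this times the t quantile.
- pMI on all treated: the m eptinezumab participants take placebo-like values, so the estimate is effect × (1 − m/285).
- pMI standard error by Rubin's rule: the drawn placebo mean is shared by both arms and cancels in the difference. Within-imputation variance is 2 × 6.2²/285 and between-imputation variance is 2m × 6.2²/285², so SE = 6.2 × √((2/285)(1 + m/285)).
- Window in which the set matters: from the FAS threshold to the pMI threshold/(1 − m/285). Its probability is computed with true effect 1.5 and the FAS standard error.
- Tipping shift: (observed effect − pMI threshold) × 285/m. This is how many days worse each excluded eptinezumab participant must be than the missing-at-random value.

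| | m = 3 | m = 9 | m = 14 |
|---|---|---|---|
| FAS SE | 0.522 | 0.528 | 0.533 |
| FAS threshold | 1.026 | 1.037 | 1.046 |
| pMI SE, all treated | 0.522 | 0.528 | 0.532 |
| pMI threshold | 1.0255 | 1.036 | 1.045 |
| pMI estimate at observed 1.50 | 1.484 | 1.453 | 1.426 |
| p-value | 0.005 | 0.006 | 0.008 |
| Window where the set matters | 1.026-1.036 | 1.037-1.070 | 1.046-1.099 |
| Probability if true effect is 1.5 | 0.6% | 1.8% | 2.9% |
| Tipping shift at observed 1.50 (days) | 45.1 | 14.7 | 9.3 |

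A shift of 45.1 days is impossible in a 28-day month. The shift depends strongly on the observed effect: with m = 14 and an observed 1.20 it is (1.20 − 1.045) × 285/14 = 3.2 days.

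**A case that crosses 0.05.** With m = 14 and an observed 1.08, the FAS gives p = 0.043. pMI on all treated gives 1.08 × (1 − 14/285) = 1.027, p = 0.054.

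**Checks by simulation.** A one-month simulation without covariates (400 trials, 200 imputations) gave pMI standard errors of 0.521, 0.527 and 0.534. A second, adjusting for baseline (1,000 runs, 20 imputations), gave rejection rates of 82.7% (FAS) against 82.2% (all treated) at 1% excluded, and 78.4% against 75.5% at 5%. The differences of 0.5 and 2.9 points match the window probabilities.

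**The case against.** The strongest reply is that this hardly matters. At the planned effect nothing changes, and the only example that crosses 0.05 combines a borderline result with the upper assumption. Entrants had to complete at least 24 of 28 screening diary days (protocol 5.3), missing diary data are expected to be mostly sporadic (protocol 16.10), and exclusion needs fewer than 14 reported days in each of three months. The pMI analysis also has no pass/fail rule, so a p-value moving past 0.05 triggers nothing. All of this stands, and it limits the point to one of scope.

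A second reply is that the SAP speaks of imputing all missing eptinezumab data, so scope is unstated rather than deliberately narrowed. That is fair, but the wording does not override an explicit default, and it shows that the default delivers less than the text intends.

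A third is transparency. SAP 6.1 plans analysis-set counts, and SAP 6.2 plans withdrawal listings with dates and reasons and Kaplan-Meier curves on treated participants. Readers will see the exclusions, but no planned analysis includes them.

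Finally, FAS membership is set at a classification meeting, and SAP version 3.0 already reflects that meeting's minutes. The blinded count may therefore have been known, and the timing of any amendment matters.

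**Conclusion.** The gap is real and follows from the text: an FAS default, a one-valid-month condition, and no other set named in 11.3.4. Its expected effect is small. For 3 to 14 excluded per arm, an observed -1.50 becomes between -1.48 and -1.43 and stays significant. The chance that the set decides whether pMI is significant at 5% is about 0.6% to 2.9% if the true effect is -1.5. It would matter only for a result close to the significance threshold. These figures rest on assumed counts, equal loss in both arms, SD 6.2 and a single-month approximation; unequal loss was not examined. The primary MMRM, hierarchy and decision rule stand. The change should be made because it is cheap and gives the robustness statement the scope it claims.

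**What to change.** - In SAP 11.3.4.1 and 11.3.4.2, name the analysis set as the APTS with a baseline MMD value. Keep the FAS for the primary MMRM.
- For participants with no valid month, impute all three 4-week periods from baseline MMDs and previous treatment failures.
- The pMI models are fitted in the placebo group, so use country only where it is estimable there; otherwise pool it or leave it out of the imputation model. SAP 18.5.6 reports very few North American participants, and the pooling rule in SAP 15.15 covers only logistic regression.
- Apply the same principle to the key secondary pMI analyses in SAP 11.4.4, using each endpoint's own baseline value as its model already does.
- Record the change in SAP section 18, because protocol 16.2 and 16.8.1 place efficacy analyses on the FAS. Make it before unblinding; if that has passed, label the analyses post hoc.

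The cost is minor programming for baseline-only rows and sparse countries, one section 18 entry, and a slightly less favourable sensitivity estimate (about -1.43 instead of -1.50 at 14 per arm). No new reporting is needed, since analysis-set counts by arm and diary gaps by interval are already planned. Randomized but untreated participants remain outside both sets.

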11.3.4.2 Assessing the impact of missing data using a tipping point analysis

To further evaluate the potential impact of missing data, a multiple imputations (MI) approach will be used to impute the missing data for all three 4-week post-baseline periods in the Placebo-controlled Period using a tipping point analysis, where the robustness of the results under

increasing deviations from missing at random (MAR) for the missing observations will be assessed.

After the use of prorating, the remaining missing data for each month will firstly be imputed through standard MI under MAR assumption. In addition, the imputed data for MMDs on eptinezumab for each 4-week post-baseline period will be adjusted by applying a range of deviations based on delta (δ) and the estimated effects for EPTI and PBO for each 4-week post-baseline period from primary analysis as follows:

$$\text{EPTI} + \delta \cdot (\text{PBO} - \text{EPTI}),$$

where δ will take values 0%, 10%, 20%, 30%, ...

Thus, the estimated effect will start from an assumption of the effect being similar to the effect in other participants treated with EPTI, and then stepwise worsen, with $\delta = 100\%$ being an assumption of participants with missing data having a similar effect as placebo. The value of δ will be increased until the p-value > 0.05 , or until the limit for the worst score possible for the missing data has been reached. In case of monthly migraine days, the score cannot be worse than 28 days with migraine out of 28 days observed. The method used for imputation, analysis of data and combination of results from analyses will match the pMI method described above (same seed numbers will also be used), except for the assumed effect for the EPTI group which will be as described in this section.

11.3.5 Subgroup Analysis for Primary Endpoint

Subgroup analyses will be performed using the model specified in Section 11.3.2 on the set of participants included in the subgroup.

The subgroups that will be investigated are:

- Sex: Female and Male
- Number of failed previous treatments: ≤ 2 and > 2

No hypothesis testing will be conducted in the subgroup analysis. Only the treatment differences relative to placebo and their associated 95% CIs will be estimated and displayed using a forest plot.

11.3.6 Exploratory Analysis of the Primary Endpoint

Two additional exploratory analyses using the alternative definitions of migraine day (1) based on daily symptoms and duration of the headache and (2) considering a mixture of headache day and migraine day in Section 3.6.1 to count and derive the MMDs will be conducted to evaluate the relevance of the different derivation strategies. The same MMRM model as that described for the primary analysis will be used to compare between EPTI and PBO averaged across Weeks 1-4.

11.4 Analysis Methodology for the Key Secondary Endpoints

11.4.1 Key Secondary Estimands

For continuous key secondary endpoints, estimands follow the same rationale and strategies as for the primary endpoint to address intercurrent events, see Section 11.3.1.

A summary of the binary key secondary estimand including intercurrent events and strategies can be found below in [Table 3](#).

Table 3 Binary Key Secondary Objective(s) and Estimand(s) with Rationale for Strategies to Address Intercurrent Events

Key Secondary Objectives	To evaluate the efficacy of eptinezumab as add-on to BI for the prevention of migraine and treatment of MOH	
Estimand Label	Estimand 2a (Key Secondary)	Estimand 2b (Key Secondary)
Estimand Description	Odds ratio of participants not fulfilling the ICHD-3 diagnostic criteria for CM nor MOH between EPTI and PBO regardless of the use of preventive migraine medication and interruptions/terminations of infusions, assuming other anti-CGRP treatment is not available.	
Target Population	Participants who suffer from migraine and MOH and who fulfil the inclusion and exclusion criteria.	
Treatment Conditions	Trial arm: BI and eptinezumab 100 mg Control arm: BI and placebo	
Endpoint	Not fulfilling the ICHD-3 diagnostic criteria for CM nor MOH (Weeks 1-4)	Not fulfilling the ICHD-3 diagnostic criteria for CM nor MOH (Weeks 1-12)
Population Level Summary	Odds ratio of participants not fulfilling the ICHD-3 diagnostic criteria for CM nor MOH between participants on eptinezumab and placebo across Weeks 1-4	Odds ratio of participants not fulfilling the ICHD-3 diagnostic criteria for CM nor MOH between participants on eptinezumab and placebo across Weeks 1-12
ICEs and Strategies		
ICE1 (new preventive medication)	Treatment policy	
ICE2 (anti-CGRP medication)	Hypothetical	
ICE3 (interruption/termination of infusion)	Treatment policy	
Rationale	A treatment policy strategy is used to estimate the treatment effect irrespective of new preventive migraine medication other than anti-CGRP treatment initiation and interruption/termination of infusions during trial period to reflect clinical practice. Under the assumption of less use of preventive migraine treatment in	

Key Secondary Objectives	To evaluate the efficacy of eptinezumab as add-on to BI for the prevention of migraine and treatment of MOH	
Estimand Label	Estimand 2a (Key Secondary)	Estimand 2b (Key Secondary)
	
the eptinezumab group compared to the placebo group, this is considered to be a conservative approach.
 
A hypothetical strategy is used to handle use of disallowed anti-CGRP medication other than eptinezumab as preventive migraine medication. This will better reflect clinical practice, since it is not standard practice to prescribe two different anti-CGRP treatments simultaneously.
	

Table 4 Key Secondary Endpoints and Analyses

Key Secondary Endpoint	Population Level Summary	Primary Analysis	Sensitivity Analysis
Change from baseline in the number of MMDs (Weeks 1-12) Change from baseline in number of MHDs (Weeks 1-4) Change from baseline in MHDs (Weeks 1-12)	The mean difference in the change of number of MMDs or MHDs from baseline between participants on eptinezumab and placebo	MMRM	pMI + MMRM
Not fulfilling the ICHD-3 diagnostic criteria for CM nor MOH (Weeks 1-4) Not fulfilling the ICHD-3 diagnostic criteria for CM nor MOH (Weeks 1-12)	Odds ratio of participants not fulfilling the ICHD-3 diagnostic criteria for CM nor MOH between participants on eptinezumab and placebo	Logistic Regression	-
Change from baseline in average Daily Pain assessment score (Week 1-2)	The mean difference in the change from baseline in average Daily Pain assessment score between participants on eptinezumab and placebo	ANCOVA	ANCOVA on the days without taking any acute migraine medications
Change from baseline in monthly days with acute migraine medication use (Weeks 1-4) Change from baseline in monthly days with acute migraine medication use (Weeks 1-12)	The mean difference in the change from baseline in acute migraine medication use between participants on eptinezumab and placebo	MMRM	pMI + MMRM

